6.2.11.2 Unsolicited Adverse Events

During all follow up visits, the occurrence of unsolicited adverse events will be assessed following an open question to participants, with the dates of commencement and resolution and any medication required. Adverse events will be followed to resolution or stabilization. They will be graded as indicated in **Appendix B**.

6.2.11.3 Routine Laboratory Parameters

Laboratory parameters will routinely include hematology (WBC and differential, hemoglobin/hematocrit, platelets), clinical chemistry (Creatinine, BUN, Total and Direct bilirubin, AST and ALT, and alkaline phosphatase), and urinalysis (protein, WBCs, RBCs and casts). Female participants will have serum beta-HCG measured at screening and on the day of each 3BNC117 and 10-1074 infusions, and urine beta-HCG checked during follow up visits. The laboratory samples for these tests will be collected at the time points indicated in the Time of Events Schedule (**Appendix A**).

In the event of an abnormal laboratory value, participants may be asked to have additional sample(s) collected at the discretion of the principal investigator or designee.

Participants will be screened for syphilis (RPR) and viral hepatitis (HBsAg and HCV viral load) at the Screening Visit. Anti-nuclear antibody will also be checked at screening.

6.2.11.4 Assays

1. Measurement of 3BNC117 and 10-1074 serum levels by sandwich ELISA will be performed at Celldex Therapeutics.

- 2. Anti-drug (10-1074) antibody responses in serum. Assays will be performed at Celldex Therapeutics Inc.
- 3. TZM-bl neutralization assay will be performed in the laboratory of [name] of the Beth Israel Deaconess Hospital in Boston (a Core Laboratory sponsored by the Collaboration for AIDS Vaccine Discovery, CAVD). *In vitro* neutralization assays with serum from study participants from all study groups, before and after administration of 3BNC117 and 10-1074 will be performed to measure 3BNC117 and 10-1074 *in vivo* neutralizing activity against a panel of pseudoviruses representative of multiple viral clades.

Optimal sample collection, processing, cryopreservation, archiving and storage will be maintained. Additional studies will be performed as warranted at the discretion of the investigators.

6.2.11.5 Pharmacokinetic evaluations

3BNC117 and 10-1074 serum levels will be measured by validated sandwich ELISA methods performed at Celldex Therapeutics. Serum samples will be collected before and at the end of each 3BNC117 and of each 10-1074 infusion, at 2 days and 1, 2, 3 and 4 weeks after respective infusions, and at later time points as outlined in **Appendix A**.

Briefly, serum samples, positive and negative controls, and multiple dilutions of a 3BNC117 or 10-1074 reference standard will be incubated in plates coated with a murine anti-idiotype antibody to 3BNC117 or a murine anti-idiotypic antibody to 10-1074 for the respective assays. Immobilized 3BNC117 will be detected with a murine anti-human IgG kappa chain mAb-HRP conjugate, and immobilized 10-1074 will be detected with an affinity-purified $F(ab')_2$ fragment goat polyclonal anti-human IgG Fc gamma chain specific-HRP conjugate. Colorimetric detection will be afforded with HRP substrate, tetra-methylbenzidine.

The concentration of 3BNC117 or 10-1074 in the samples will be interpolated from a standard curve of 3BNC117 or 10-1074, using a logistic curve-fitting algorithm. The reference standard and positive controls will be created from the drug product lot of 3BNC117 or 10-1074.

Pharmacokinetic parameters, including AUC, Cmax, $T_{1/2}$, Tmax and others will be estimated by performing a non-compartmental analysis (NCA) using WinNonlin 6.3. ANOVA model will be used to compare cohort differences for AUC and Cmax. The dose proportionality for the 2 parameters (AUC and Cmax) will be examined by regression analysis. Exposure parameters will be compared between single-and multiple-dose regimens to evaluate the extent of drug accumulation and the impact on clearance. Pharmacokinetic parameters will be examined to correlate exposure with safety and pharmacodynamic parameters (decline in plasma HIV-1 RNA), and variance, based on population intrinsic factors such as weight and gender, will be explored. In addition, we will compare pharmacokinetic parameters when 3BNC117 and 10-1074 are given in combination to historical monotherapy data with either antibody.

7 Investigational Products

Investigational Drug Name:	3BNC117
Manufacturer name of drug:	Celldex Therapeutics, Inc.
IND Number:	118,225
IND Sponsor:	[name]
Investigational Drug Name:	10-1074
Manufacturer name of drug:	Celldex Therapeutics, Inc.
IND Number:	123,713
IND Sponsor:	[name]

7.1 Regimen

3BNC117 and 10-1074 will be administered intravenously at 3 or 10 mg/kg.

- Group 1: one infusion of 3BNC117 and 10-1074 at day 0, each dosed at 10 mg/kg.
- Group 2: three infusions of 3BNC117 and 10-1074, each dosed at 3 mg/kg, at day 0, weeks 8 and 16.
- Group 3: three infusions of 3BNC117 and 10-1074, each dosed at 10 mg/kg, at day 0, weeks 8 and 16.

7.2 Study Product Formulation and Preparation

3BNC117 is provided by Celldex Therapeutics in single-use vials containing 5 ml of 3BNC117 at a 20 mg/ml concentration. 3BNC117 will be diluted in normal saline (NaCl 0.9%) to a volume of 100 ml.

10-1074 is provided by Celldex Therapeutics in single-use vials containing 5 ml of 10-1074 at a 20 mg/ml concentration. 10-1074 will be diluted in normal saline (NaCl 0.9%) to a volume of 100 ml.

Sodium chloride 0.9% provided from a commercial source will be used as the placebo at a volume of 100ml.

7.3 Dispensing and Handling of Investigational Product

3BNC117 and 10-1074 will be shipped from Celldex Therapeutics and will be stored in the RUH Pharmacy at 2 - 8°C. Both products will be dispensed by the RUH pharmacist. Trial personnel will ensure that the study ID number on the infusion bag matches the study ID assigned to the participant prior to administration.

The appropriate dose will be calculated by the RU pharmacist according to study allocation and participant's weight. Both products will be dispensed in a piggy-back, diluted in normal saline (NaCl 0.9%), ready for administration by the study investigators.

7.4 Accountability and Disposal of Used and Unused Investigational Product

The date, allocation number and location of storage of the vials will be recorded in a log. During the trial, the product accountability form, and the dispensing log will be monitored. At the end of the trial, unused vials will be returned to Celldex Therapeutics or destroyed.

8 Data Analysis

8.1 Analysis of Safety, PK and Antiretroviral effects

Primary Outcomes

- Safety: The safety population will include all participants who receive placebo or 3BNC117 and 10-1074 infusions. A baseline measurement and at least one laboratory, vital sign, or other safety-related measurement obtained after placebo or 3BNC117 and 10-1074 infusions may be required for inclusion in the analysis of a specific safety parameter.

The number and percentage of participants experiencing one or more AEs will be summarized by study group, relationship to study drug, and severity. AEs will be summarized by the number and percentage of participants who experienced the event, according to system organ class (SOC) and preferred term. AEs will also be summarized by severity grade and by relationship to study drug according to the Toxicity Grading Scale for Healthy Adult and Adolescent Volunteers Enrolled in Preventive Vaccine Clinical Trials. The CTCAE v4.03 grading scale will be used for reporting and grading adverse events related to infusion reactions and cytokine release syndromes in all groups (**Appendix B**). Changes in hematology, chemistry, and other laboratory values will be summarized descriptively. Changes will be calculated relative to the values collected at baseline.

- Pharmacokinetic parameters will be calculated using standard non-compartmental analysis methods. Descriptive results will be presented for the pharmacokinetic parameters by the 3 study groups. Pharmacokinetic parameters, including AUC, Cmax, $t_{1/2}$, Tmax and others will be summarized using descriptive statistics. ANOVA model will be used to compare group differences for AUC and Cmax. Regression analyses will be performed with AUC and Cmax as dependent variables and dose group as an independent variable. Population intrinsic factors, such as weight and gender, will be included in the regression models to assess whether these factors modify the relationship between dose and pharmacokinetic parameters.

Secondary outcomes

- Anti-10-1074 antibodies: The frequency of induced anti-3BNC117 and anti-10-1074 antibodies at 8 weeks following each infusion will be reported for all 3 groups and the proportion will be compared using Fisher's Exact test. The levels of the anti-antibodies will be compared using ANOVA or Kruskal-Wallis test.

Exploratory measurements

- In vitro neutralization assays will be performed with serum from study participants to evaluate antiretroviral activity against Tier 1 and Tier 2 HIV strains. Results will be descriptive.

The analysis of study data will be primarily descriptive, with emphasis on tabular and graphical displays. This study is exploratory, and any statistical inferences will be hypothesis generating and not confirmatory.

8.2 Sample Size Considerations

Safety:

The safety population will include all participants who receive at least one dose of study treatment. A baseline measurement and at least one laboratory, vital sign, or other safety-related measurement obtained after at least one dose of study treatment will be required for inclusion in the analysis of a specific safety parameter.

With 6 placebo participants, the 95% upper binomial confidence limit for the proportion with adverse events is 46%. For the proposed 18 participants when combining all three study treatment groups, the upper limit for the proportion with adverse events is 19%. The table below shows the upper 95% confidence limits for the binomial proportion when no event has been observed for sample sizes ranging from 6 to 20.

Table 1. Safety assessments: Upper 95% confidence limits for the binomial proportion							
Sample Size	Proportion	Sample Size	Proportion	Sample Size	Proportion		
6	0.46	11	0.28	16	0.21		
7	0.41	12	0.26	17	0.20		
8	0.37	13	0.25	18	0.19		
9	0.34	14	0.23	19	0.18		
10	0.31	15	0.22	20	0.17		

The Fisher's exact test will be used to compare the proportion of adverse events in the placebo and treatment groups.

Pharmacokinetics:

The 95% margin of error for estimating the mean elimination half-life of 3BNC117 plus 10-1074 is summarized below for Group 2 (n=6) and Group 3 (n=6) based on standard deviations from 4.5 days to 8.0 days using the pharmacokinetics data of 3BNC117 administered alone at 3 mg/kg and 10 mg/kg in healthy participants.

Table 2. Pharmacokinetics: 95% margin or error for estimating mean elimination half-life

 of the study products

Number of	Standard deviation (days)	95% margin of error (+/- days)		
participants				
6	4.5	3.6		
	5.0	4.0		
	5.5	4.4		
	6.0	4.8		
	6.5	5.2		
	7.0	5.6		
	7.5	6.0		
	8.0	6.4		
12 (Groups 2 and 3)	4.5	2.5		
	5.0	2.8		
	5.5	3.1		
	6.0	3.4		
	6.5	3.7		
	7.0	4.0		
	7.5	4.2		
	8.0	4.5		

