The study will be conducted under a placebo-controlled, double blind, randomized allocation of the study products. Study participants in each study group will be randomized to receive intravenous infusions of 3BNC117 and 10-1074 or placebo. 3BNC117 and 10-1074 will be administered at 2 dose levels (3 mg/kg and 10 mg/kg). These doses were selected based on the planned development of subcutaneous formulations for the prophylactic use of these products. The study will consist of 3 groups (Figure 1). Enrollment in Group 1 will begin first and participants will be enrolled at least one day apart. Eight participants will be enrolled in each group; 6 will be randomized receive the study drugs and 2 will be randomized to receive placebo. Participants in Group 1 will receive a single infusion of each antibody at 10mg/kg at Week 0. Enrollment in Group 2 will begin only after Day 28 safety data from all participants in Group 1, including ophthalmologic exams, are available. Enrollment in Group 3 will begin only after the Day 28 safety data from all participants in Group 2 is available. If > 1 grade 3 or higher adverse events deemed probably or definitely related to the study drugs occurs in a single group, the next group will not be enrolled pending SMC review. Participants in Groups 2 and 3 will receive 3 infusions of each antibody at

Weeks 0, 8, and 16, at a dose of either 3mg/kg or 10mg/kg. The antibodies will be administered sequentially via intravenous infusion. Each antibody will be administered over 60 minutes.

Figure 1. Study Design

* Enrollment in subsequent group may begin following review of Day 28 safety data from all subjects in the previous group

Following product infusions, study participants will return for safety assessments at multiple time points. Blood samples will be collected for safety testing at weeks 1, 2, and 4 following each infusion, then at multiple time points until the end of study follow up.

Baseline pharmacokinetic assessments will be performed before the start of the first infusion. Peak PK sampling for 3BNC117 will occur following the completion of the 3BNC117 infusion prior to the start of the 10-1074 infusion. Peak PK sampling for 10-1074 will occur following the completion of the 10-1074 infusion. Additional PK assessments will occur at multiple time points during study follow up, as outlined in **Appendix A**. Study participants will be followed for a total of 24 weeks following the final antibody infusion.

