6.2.2 Randomization

This study is randomized and double-blinded. Randomized treatment assignments will be generated by the Rockefeller University Hospital pharmacy. The 8 participants in each group will be randomized in a ratio of 6 study drug recipients to 2 placebo recipients. Randomization will be generated using SAS 9.4. Blinding will not apply to the assignment of dose levels (3 or 10 mg/kg). The study preparation will be provided to the study nurses for injection under a coded, masked identification. The placebo and mAb preparations will be indistinguishable in the preparation provided for participants. The nurses, study staff, investigators, and participants will be blinded as to the identity of the study preparation. Participants will be unblinded at the end of the study. To accomplish this, study nurses will be provided with the randomization code after the study has been completed, and they will notify each participant. In the event of a medical emergency wherein knowledge of the treatment assignment will influence the participant's care, the Principal Investigator may unblind the treatment assignment.

6.2.3 3BNC117 and 10-1074 Administration Procedure

3BNC117 is provided in single-use vials containing 5 ml of the product at a concentration of 20 mg/ml. The volume of 3BNC117 to be administered will be calculated by the site research pharmacist, according to study assignment. The appropriate volume of 3BNC117 will be diluted in sterile normal saline to a total volume of 100 ml, and will be administered as an intravenous infusion over 60 minutes.

10-1074 will be provided in single-use vials containing 5 ml of the product at a concentration of 20 mg/ml. The volume of 10-1074 to be administered will be calculated by the RUH research pharmacist, according to study assignment. The appropriate volume of 10-1074 will be diluted in sterile normal saline to a total volume of 100 ml and will be administered as a slow intravenous infusion over 60 minutes.

- Sterile saline, NaCl 0.9% (placebo) will be dispensed in a volume of 100 ml, and will be administered as a slow intravenous infusion over 60 minutes. A second bag of sterile saline will be administered after the infusion of the first saline bag is completed and the line is flushed.

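### The adverse-event comparison in section 8.2 ignores the groups within which participants are randomized; it should be stratified by group and stated to be all active versus all placebo (minor)

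*Protocol*

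**What the plan says.** Section 6.2.2 randomizes within group: "The 8 participants in each group will be randomized in a ratio of 6 study drug recipients to 2 placebo recipients". Section 4 sets different exposure by group. For Group 1: "Participants in Group 1 will receive a single infusion of each antibody at 10mg/kg at Week 0". For the others: "Participants in Groups 2 and 3 will receive 3 infusions of each antibody at" Weeks 0, 8 and 16. On follow-up: "Study participants will be followed for a total of 24 weeks following the final antibody infusion". That gives 24 weeks in Group 1 and 16 + 24 = 40 weeks in Groups 2 and 3.

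Section 8.2 gives precision for two pooled samples: "With 6 placebo participants, the 95% upper binomial confidence limit for the proportion with adverse events is 46" percent, and "For the proposed 18 participants when combining all three study treatment groups, the upper limit for the proportion with adverse events is 19" percent. It then names the test: "The Fisher's exact test will be used to compare the proportion of adverse events in the placebo and treatment groups". It does not say whether the three active groups are pooled or taken one at a time, and it gives no stratification and no adverse-event window. The protocol summary repeats the test.

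Section 8.1 is descriptive: "The number and percentage of participants experiencing one or more AEs will be summarized by study group". It also declares all inference exploratory. Section 3.6 makes adverse events in the week after infusion a primary outcome and those over the whole follow-up a secondary one.

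**The concern.** Group carries real differences in the chance of having at least one adverse event. A participant in Group 2 or 3 has three one-week windows and 40 weeks under observation; a participant in Group 1 has one window and 24 weeks. Section 6.1.3 adds an ascertainment difference: adverse events are recorded at 1 and 4 hours after infusion in Group 1, but at 1 hour only in the others.

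Two consequences follow. First, an unstratified test uses a reference distribution in which the active and placebo arms could differ in their mix of groups. The fixed 6:2 split rules that out, so the test allows for variation that the design has removed and loses sensitivity. Second, if the plural in the Fisher sentence were read as each group against the 6 pooled placebos, the placebo arm would have a different exposure mix from the group it is compared with. The primary objectives treat single-infusion and three-infusion tolerability separately, so an analyst might well try such contrasts.

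**Working it through.** **The plan's own figures.** With 0 events among n, the upper limit of a two-sided exact 95% interval is 1 − 0.025^(1/n). For n = 6 this is 0.459 and for n = 18 it is 0.185, matching the stated 46% and 19%. All 15 entries of Table 1 agree to rounding. Section 8.2 thus works with participants as the unit and with pooled samples of 6 and 18.

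**Inputs.** From the protocol: 6 active and 2 placebo per group; 1, 3 and 3 infusion visits; 24, 40 and 40 weeks. The protocol gives no adverse-event rates, so the risks below are assumptions.

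**Pooled comparison, no drug effect.** Let p be the risk per infusion. The risk of at least one event is p in Group 1 and 1 − (1 − p)^3 in Groups 2 and 3. At p = 0.20:

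- Groups 2 and 3: 1 − 0.8^3 = 0.488
- All placebo: (2 × 0.20 + 4 × 0.488)/6 = 0.392
- All active: (6 × 0.20 + 12 × 0.488)/18 = 0.392

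The difference is 0. This holds at every p, because each arm is one third Group 1 and two thirds Groups 2 and 3.

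**One group against all 6 placebos, no drug effect.**

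| Assumed p per infusion | Group 1 | Groups 2, 3 | Pooled placebo | Group 1 minus placebo | Group 2 or 3 minus placebo |
|---|---|---|---|---|---|
| 0.10 | 0.100 | 0.271 | 0.214 | −0.114 | +0.057 |
| 0.20 | 0.200 | 0.488 | 0.392 | −0.192 | +0.096 |
| 0.30 | 0.300 | 0.657 | 0.538 | −0.238 | +0.119 |
| 0.50 | 0.500 | 0.875 | 0.750 | −0.250 | +0.125 |

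If risk accrues by week instead, Groups 2 and 3 have 1 − (1 − p)^(40/24). For Group 1 risks of 0.1 to 0.7, the shifts are −0.04 to −0.12 for Group 1 and +0.02 to +0.06 for Group 2 or 3. In all these scenarios the two-sided Fisher rejection rate stays at or below about 0.022. The harm would be a shifted estimate, not false positives.

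**Stratified versus pooled test.** The stratified test conditions on the number of participants with an event in each group. Its statistic is the total number of active participants with an event, and its null distribution is the convolution of three hypergeometric distributions (6 of 8 active in each). Both tests were enumerated exactly at two-sided 0.05, ordering outcomes by probability, as Fisher's test usually does.

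| Assumed risk per infusion, placebo vs active | Pooled Fisher | Stratified exact |
|---|---|---|
| 20% vs 20% (size) | 0.014 | 0.023 |
| 5% vs 30% (power) | 0.27 | 0.37 |
| 10% vs 50% (power) | 0.51 | 0.62 |
| 20% vs 60% (power) | 0.43 | 0.47 |

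For null risks from 5% to 50% per infusion, the size of the stratified test is at most 0.024. If both two-sided p-values are instead defined by doubling the smaller tail, the powers are 0.27 vs 0.28, 0.46 vs 0.53 and 0.32 vs 0.37. The gain keeps its direction but is smaller in the first scenario.

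**Same-group contrasts.** With 6 active and 2 placebo, the smallest attainable p-value is 1/28 = 0.036, reached only at 6/6 versus 0/2 or the reverse.

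**The case against.** A reader might infer that the planned comparison is biased by exposure. The documents do not support that. The sentences just before the Fisher test describe 6 placebo and 18 combined active participants, so the natural reading is the pooled comparison, whose null difference is exactly 0. No sentence plans a single group against all 6 placebos, and section 8.1 does not specify a pooled-placebo column in its by-group summary.

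Departures from 3:1 would be slight. The safety population keeps everyone who was dosed. Section 10 allows only 2 extra participants: if both were active in Group 3 at p = 0.20, the active proportion would be (6 × 0.20 + 14 × 0.488)/20 = 0.402, against 0.392 in placebo.

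Two further inferences also fail. Counting events rather than participants is not a fair reading, because section 8.1 counts participants. And 24 versus 40 weeks does not affect the one-week primary outcome, although one versus three windows does if it is scored once per participant.

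It can also be said that stratification is detail for an analysis plan, that 2 placebo participants per stratum is very few, and that the study is exploratory. These points limit the priority. They do not remove the suggestion: the protocol does name a test, that test omits the randomization factor, and the stratified alternative performed better in each scenario examined when the two p-values were defined alike.

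**Conclusion.** The point stands as a minor improvement. The pooled test is valid and unbiased under 6:2 allocation in every group, but it is more conservative than it needs to be. Under the assumed risks, stratifying adds about 0.04 to 0.12 of power with the usual ordering (0.01 to 0.07 with doubled tails), and size stays at or below 0.024. These gains rest on assumed per-infusion risks, independent infusions and full compliance.

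Confounding by exposure arises only if the wording is taken to mean each group against all 6 placebos. At an assumed 20% per infusion it would make Group 1 look 19 points better than placebo and Groups 2 and 3 look 10 points worse, with no drug effect. The sign follows from the design; the size depends on the assumption. Section 8.2 should rule that reading out.

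**What to change.** In section 8.2, and in the matching sentence of the protocol summary, state that:

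- the comparison is the proportion of participants with one or more adverse events, all active versus all placebo, by an exact conditional test of Mantel-Haenszel type stratified by study group, with the definition of the two-sided p-value named;
- by-group contrasts are descriptive, or use only same-group placebo (n = 2) or, for Groups 2 and 3, their own exposure-matched placebo (n = 4);
- the 7-day outcome is also shown after the first infusion only, so that all three groups have one window each.

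This costs a few sentences and slightly more analysis work. It needs no new data, visits or participants, and the inference remains exploratory.

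### Table 2 (Protocol 8.2) states 95% margins for mean half-life with the normal multiplier 1.96 at n=6 and n=12; t-based margins are 31% and 12% larger

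*Protocol*

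**What the plan says.** Section 8.2, under Pharmacokinetics, introduces Table 2 with "The 95% margin of error for estimating the mean elimination half-life of 3BNC117 plus 10-1074 is summarized below for Group 2 (n=6" and continues "and Group 3 (n=6) based on standard deviations from 4.5 days to 8.0 days". The SDs are obtained "using the pharmacokinetics data of 3BNC117 administered alone at 3 mg/kg and 10 mg/kg in healthy participants". The first block of the table is for 6 participants and the second is labelled "12 (Groups 2 and 3". The heading of the last column repeats the 95% claim. The section names no multiplier, does not say that the SD is treated as known, and does not mention a normal approximation.

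The group sizes follow from section 6.2.2: "The 8 participants in each group will be randomized in a ratio of 6 study drug recipients to 2 placebo recipients". Section 3.6 lists elimination half-life within a primary outcome. Section 8.1 says of the analysis: "Descriptive results will be presented for the pharmacokinetic parameters by the 3 study groups".

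**The concern.** A 95% margin for a mean can use 1.96 only if the SD is known or the sample is large. Neither holds here. The protocol tabulates a range of SDs because the value is uncertain, and that range comes from one antibody given without the other. Any margin reported for these groups will rest on an SD estimated from 6 or 12 people.

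Half-life belongs to a primary outcome, and Table 2 is the only statement of how precisely it will be estimated. In a study that is mainly descriptive, that statement carries the sample-size rationale for pharmacokinetics. If it is too favourable, a reader expects tighter estimates than the groups can deliver.

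**Working it through.** **Inputs**
- n = 6 and n = 12; SD 4.5 to 8.0 days in steps of 0.5 (section 8.2, Table 2).
- Two-sided 95%, from the table's own label and its +/- column.

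**Step 1. Reproduce the printed table.** Try half-width = 1.96 × SD/√n.
- n=6, SD 4.5: 1.96 × 4.5/2.449 = 3.60. SD 8.0: 1.96 × 8.0/2.449 = 6.40.
- n=12, SD 4.5: 1.96 × 4.5/3.464 = 2.55. SD 8.0: 1.96 × 8.0/3.464 = 4.53.

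To one decimal, all 16 entries agree (the n=12, SD 4.5 value is 2.546 before rounding, printed as 2.5). Two-sided t, one-sided 95% t (2.015 and 1.796) and a multiplier of 2 do not reproduce the table. At n=6, SD 4.5, they give 4.7, 3.7 and 3.7 against the printed 3.6.

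**Step 2. Use the multiplier for an estimated SD.** Half-width = t(0.975, n−1) × SD/√n, with t = 2.571 on 5 df and 2.201 on 11 df.

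| SD (days) | n=6 printed | n=6 with t | n=12 printed | n=12 with t |
|---|---|---|---|---|
| 4.5 | 3.6 | 4.7 | 2.5 | 2.9 |
| 5.0 | 4.0 | 5.2 | 2.8 | 3.2 |
| 5.5 | 4.4 | 5.8 | 3.1 | 3.5 |
| 6.0 | 4.8 | 6.3 | 3.4 | 3.8 |
| 6.5 | 5.2 | 6.8 | 3.7 | 4.1 |
| 7.0 | 5.6 | 7.3 | 4.0 | 4.4 |
| 7.5 | 6.0 | 7.9 | 4.2 | 4.8 |
| 8.0 | 6.4 | 8.4 | 4.5 | 5.1 |

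**Step 3. Size of the difference (ratio of multipliers, before rounding).**
- Increase over the normal-based margin: 2.571/1.960 = 1.31 (n=6); 2.201/1.960 = 1.12 (n=12).
- Shortfall against the t-based margin: 1 − 1.960/2.571 = 24% (n=6); 1 − 1.960/2.201 = 11% (n=12).

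**Step 4. Coverage of mean ± 1.96 × s/√n, with s estimated.**
- n=6: P(|t| < 1.96) on 5 df = 0.893. It misses 10.7% of the time, and 10.7/5 = 2.1 times the claimed rate.
- n=12: P(|t| < 1.96) on 11 df = 0.924. It misses 7.6% of the time, and 7.6/5 = 1.5 times the claimed rate.

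**Step 5. Sensitivity to convention.**
- If Groups 2 and 3 are pooled with a within-group SD, the df are 10, t = 2.228, and the n=12 factor is 2.228/1.960 = 1.14.
- The average half-width of a t interval also includes the small-sample bias of s (about 0.952 at n=6 and 0.978 at n=12). That gives 1.31 × 0.952 = 1.25 and 1.12 × 0.978 = 1.10 times the normal-based margin.

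Under each of these conventions the printed figure is too small.

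**The case against.** The best defence is that Table 2 is a planning table conditional on assumed SDs. For a given true SD and normal data, the sample mean lies within 1.96 × SD/√n of the true mean with probability exactly 95%, so each row is correct as a statement about the sampling spread of the estimator. That much stands. It does not rescue the label, because the section never says the SD is taken as known, and the trial cannot report a margin on that basis. Table 1 in the same section uses exact binomial limits (1 − 0.025^(1/6) = 0.46 at n=6), so small-sample methods were applied there but not here.

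It is also fair to say that section 8.1 calls the study exploratory and its inferences hypothesis-generating, that no test, decision rule or sample size is derived from Table 2, and that interval methods may be set out in a statistical analysis plan that is not at hand. These points limit the weight of the error without removing it.

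A reader might go on to infer that Table 2 wrongly leaves out Group 1 and needs a row for all 18 active participants. The protocol does not support that. Group 1 also has 6 active participants, so the n=6 rows already give its precision, and section 8.1 plans no pooling of half-life over three groups that mix single-dose and three-dose regimens.

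**Conclusion.** The label and the figures do not match. As the 95% margin obtainable when the SD is estimated, every entry in Table 2 is too small. The t-based margins exceed the normal-based ones by 31% at n=6 and 12% at n=12 (14% with 10 df). This takes the SD range as given and assumes roughly normal half-lives with no loss of participants. The t column evaluates the margin at the assumed SD; the average-width convention in step 5 gives 25% and 10%.

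Three stronger readings are tempting and do not hold. The printed entries are not 31% and 12% below the t-based values; measured on that base the shortfalls are 24% and 11%. The miss rate is about double the claim only at n=6; at n=12 it is about one and a half times. And the error does not undermine the design, since nothing is decided from this table. Severity is minor to moderate.

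**What to change.** Replace the margins in Table 2 with t-based values at the same assumed SDs, and add a note naming the multiplier and df:
- n=6 (5 df): 4.7, 5.2, 5.8, 6.3, 6.8, 7.3, 7.9, 8.4 days.
- n=12 (11 df): 2.9, 3.2, 3.5, 3.8, 4.1, 4.4, 4.8, 5.1 days. If a within-group pooled SD is intended, use 10 df, which makes these slightly larger.

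The note can also say that the n=6 rows apply to Group 1. No n=18 row is needed. Keeping the printed figures with a footnote that the SD is treated as known would make the table internally honest, but it would still not show the precision the trial can report, so restating is preferable.

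The cost is one table and a sentence. The stated precision becomes less favourable; sample size, design and conduct do not change.
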